## **F. Protection of Human Subjects**

### **Risks to Human Subjects**

#### **a. Human Subjects: Involvement, Characteristics, and Design**

A purposive sample of patient-nurse dyads will be enrolled in this study. Participants in this study are minority patients with life limiting illness (cancer, COPD, or heart failure) and their health care nurses. We expect to enroll 24 minority patients with life limiting illness and 18 nurses who are directly involved in the care of the patient. The principal investigator (PI) will enroll all participants after each of them voluntarily decide to become a participant.

**Patients.** Each patient participant will engage in two audio-recorded interviews lasting approximately 60-90 minutes. For the first interview, through a narrative analysis framework, the patients will answer open-ended questions related to their illness experiences and how their illness has impacted their emotions, relationships and spirituality. (See Appendix A-Storytelling Interview Guide). For the second interview, the patient will answer exit interview questions to capture their experience of the storytelling intervention. For the patient interviews, the location will include their private inpatient room or private conference room in the facility. If the patient is discharged prior to the second exit interview, the exit interview may take place over the telephone. (See Appendix B-Exit Interview Guide).

**Nurses.** The nurses will be interviewed once. This interview will capture exit interview data related to the storytelling intervention. The participant and nurse will be interviewed at separate times. For the nurse interview, the PI will coordinate a convenient and private place to conduct the interview which might include nurse's office or private conference in the facility. (See Appendix B- Exit Interview Guide). For the usability testing, the PI will coordinate a convenient time between at the nurse's convenience to conduct the user-task-system-environment evaluations.

The following characteristics will determine the eligibility for patient participants and nurse participants. Eligibility criteria will first be determined by the patient participant, who must be:

- (1) Over age age 18
- (2) Able to speak English
- (3) Be capable of giving informed consent
- (4) Self identify as being a racial/ethnic minority and
- (5) Have one of the following LLI: cancer, COPD, or heart failure.

Eligibility criteria for the nurses are that they be:

- (1) Nurses will be at least age 18
- (2) Able to read, speak and write English
- (3) Confirm verbally that they were involved in the care of the patient who received the storytelling intervention.

Data collection activities for patient participants include completing the storytelling intervention via a 60-90 minute audio-recorded interview and completing an exit interview via a 60-90 minute audio-recorded interview. Data collection activities for the 12 nurse participants will include completing a 60-90 minute exit interview via an audio recorded interview. For the usability testing, data collection will include testing of the EHR interface with the bedside nurses and completion of a short questionnaire at the end of the hour session.

**Setting:** The participants will be recruited through the University of Colorado hospital.

b. **Sources of Materials**

Data for this proposed project will only be collected by the PI. Materials include audio-recordings of interviews, field notes, and correspondence (i.e., memos, emails) with research team members. A total of 60 audio-recorded interviews will be collected; 24 interviews for the storytelling intervention; 24 for the patient exit interviews, 12 for the nurse exit interviews. Safeguards for protecting anonymity of participants will include creating a master list of names with corresponding numbers assigned to participants at the time of the screening by the PI. Once assigned, the corresponding numbers will then be used to de-identify the remainder of participants' personal information and each participant's interview transcript. Only de-identified transcripts of interviews will be available for the remainder of the research team for analysis and interpretation processes.

All data will stored electronically on password-protected servers, folders and files, and only study staff and the investigators will have access to these study-related electronic files. Weekly assessment data will be entered into separate electronic databases directly by study staff from the paper or phone interview data collection. To obtain the patient's medical records data, we will create and maintain a separate, password-protected file of a data matching key with the names, medical record numbers, dates of admission, and study ID number for each participant. We will request electronic data for the enrolled participants from the staff who maintain the clinical data bases and match the data to the study ID number. Once all data have been matched and we have a complete set with only study identifiers (names and medical records numbers will be deleted), we will destroy the key linking study identifiers to personal identifiers for the enrolled patients. This will happen no later than the end of the study period.

The digital audio files and transcripts of the qualitative interviews will be reviewed and edited to remove all identifying information (such as names, places, or specific unique details of the patient or nurse). Original recordings and transcript files will be destroyed when the final usable set of transcripts is complete, also no later than the end of the study period.

c. **Potential Risks**

There are minimal risks to participants who elect to participate in these studies.

Physical. Participants could become fatigued during the 60-90 minutes storytelling interview process; the 30-45 minutes exit interview process and/or outcome measures data collection procedures. In this event, the researcher will encourage rest periods or if necessary reschedule a return visit to complete the interview. For the burden of time, each patient will receive \$50 in appreciation for completing the Storytelling intervention and

then again at the time of the exit interview. For the burden of time, each nurse will receive \$100 in appreciation for completing the study.

*Psychological.* For the patient participants, there is minor/moderate/severe risk for psychological distress due to the sensitive topics of life limiting illness. We will assure that participants understand both orally and in writing that they are free to decline participation in any of all study activities at any time, including declining to answer specific questions, refusing participation in the intervention, requests to speak off the record, or complete withdrawal from the study. If any of the interview or psychometric assessment data reveal increased participant distress, dissatisfaction or any adverse event, the data collection will cease. If the participant exhibits any verbal or non-verbal distress, the PI will allow the participant to stop the interview, reschedule for return visit to complete interview, or allow participant to withdraw consent. If moderate distress is exhibited, the researcher will assist in referring participant for emotional support either through family, friends, or medical nurses for follow-up related to the participant's distress. If severe distress, such as suicidal ideation is noted, the researcher will immediately refer for further work-up and care. The PI will carry a list of contact phone numbers for such referrals. If any moderate or severe distress is noted, this will be reported immediately to the primary mentor and co-mentor for help in determining if the event meets criteria for a reportable adverse event. If deemed serious adverse event, the IRB will be notified and the participant's involvement in the research study will be discontinued. Participants will be able to contact the PI to discuss any concerns or questions at any time during their participation in the study. We anticipate these to be rare events, given the nature of the data collection procedures.

*Social.* One primary concern is the possible perception of coercion due to participant recruitment occurring in health care settings. We will attempt to avoid perception of coercion by emphasizing the voluntary nature of participation and the ability of the participants (patient or nurse) to withdraw at any time without penalty. Participants could feel pressured to participate in the proposed project. The researcher will arrange with the participants a private location with only researcher and participant present for collection of the interview. Once in this private setting, the PI will remind them that participation is voluntary and that they may withdraw from the project at any time without any penalty or prejudice.

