**K99 Phase: Storytelling Intervention Design (Define and Refine)**

**Specific Aim 1:** Identify barriers and facilitators for the storytelling intervention from the perspectives of the key stakeholders—minority patients with LLI and acute-care bedside nurses—through patient and nurse exit interviews; and field analysis of EHR interface use and end-user surveys of the nurses.

**Specific Aim 2:** Conduct usability testing, applying a user-task-system-environment evaluation process to determine essential requirements for integration and use of the patient-centered story into the EHR, from the perspective of an important end user: the acute-care bedside nurse.

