## B. Description of Populations to be Enrolled.

**Setting/sample.** This study will take place at University of Colorado hospital. The participants will be minority patients with LLI and their bedside nurses. Purposeful sampling strategies will be used to recruit participants. The plan is to obtain consent from 24 patient participants equally divided (8 patients each) among three diagnostic groups: cancer, COPD, and heart failure. Data will also be collected from 12 nurse participants who provided care to the participating patients. The small sample size was chosen to be consistent with both qualitative data analysis techniques and usability data analysis techniques.

**Patient eligibility criteria.** Patients will be 18 years of age or older; able to read English; capable of giving informed consent; self-identifying as part of a racial or ethnic minority; and diagnosed with at least one LLI. The operational definition of LLI eligible for this study includes the following diagnoses: (1) metastatic solid cancer or inoperable lung cancer; (2) COPD with FEV1 values < 35% predicted or oxygen dependence; (3) New York Heart Association Class III or IV heart failure (CHF). The disease criteria were chosen to identify groups of patients with a median survival of about 2 years. These diagnoses represent 3 of the major causes of death related to LLI in the United States. Due to the nature of the qualitative design and geographical location census data, a broad group of racial/ethnic groups will be eligible to participate to allow for maximum variation sampling to collect acceptability data from a variety of groups.

[figure not shown]
**Nurse eligibility criteria.** All participating nurses will be 18 years of age or older and able to read English, and will confirm verbally that they were involved in the care of a patient who is participating in the storytelling intervention. Bedside nurses were specifically chosen as provider participants due to amount of time they interact with inpatients and the frequency with which they interface with the EHR compared to other team members. In future R01 studies of this intervention, other members of the patient's care team will be added.

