#### **D. Data Collection/Analysis.**

**Specific Aim 1: Barriers and facilitators.** Two weeks after the meta-story is added to the EHR, both patient and nurse will be contacted for exit interviews to collect information about barriers and facilitators of the intervention (see Appendix D. Exit Interview Guide). The transcribed exit interviews will be entered into ATLAS.ti (a qualitative data management/analysis program). An interpretive approach will inform the understanding of the patients' and nurses' perspectives related to barriers and facilitators. Open coding, which allows codes to form patterns as they emerge from the transcripts, will be used for the thematic analysis. An inductive approach to coding, through the use of the participant's actual words, will be used for up to 3 transcripts. Once the initial codes are chosen, the transcripts will be read again through an iterative process defined as "a movement back and forth through" data coding for creating thematic analyses.54(p86) As PI, I will complete the preliminary coding for each transcript. Then the research team, which includes my primary mentor, [name], and my co-mentor, [name], will review my preliminary codes. Once the first 3 transcripts are coded, the research team will analyze the preliminary codes across the remainder of the transcripts. Throughout the entire analytical process, the codes will be refined and defined more clearly. At each of the monthly research team meetings, codes can be expanded or similar codes collapsed into larger codes as part of the iterative process for arriving at the final themes. To ensure the rigor of the data analysis, Sandelowski's criteria for trustworthiness (credibility, applicability, consistency, and neutrality) will be used.

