For user-centered testing, I will recruit 6 nurses to test the workflow processes. The participating nurses will (1) provide content expertise of the workflow processes, and (2) put the storytelling intervention through in-house usability testing to check the "strength" of the EHR features as well as the level of user-friendliness. The goal is to make using the storytelling intervention as intuitive as possible. Prior research shows that testing with 5 participants identifies 85% of usability issues. Testing will assess ease of use, relevance and appeal, efficiency, error frequency and severity, and subjective satisfaction with the presentation of the meta-story in the EHR. Following the session, the participants will be debriefed and asked to complete a questionnaire modeled after the System Usability Scale (SUS), which asks them to rank their experience and satisfaction

with specific elements (such as where the meta-story is labeled and presented in the EHR, technical difficulties, use of the material, trust in the material, and ability to navigate within the EHR).

**Expected Outcomes.** The expected outcomes of the phase will be the completed design of a patient-centered storytelling intervention. Understanding of the patterns of barriers and facilitators of the storytelling experience from the perspectives of the key stakeholders, and evaluating the usability of the EHR integration, will inform the development of the intervention.

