study. (See letters of support by [name] and [name], UC Health Research Administration).

The written consent forms will inform patients and nurses about their own participation in study activities, including randomization, participation in the intervention, and data collection and the risks and benefits of participation. The consent form for the patient participants will also include a section describing the possibility of being selected to participate in the optional qualitative exit interviews to be scheduled after the intervention. Patients and nurses will receive

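### Does the stop for participant dissatisfaction cut off the criticism that the Aim 1 exit interviews are meant to collect?

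*Protocol*

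**What the plan says.** The sentence at issue is in Protocol section IV.F, Potential Risks, under Psychological: "If any of the interview or psychometric assessment data reveal increased participant distress, dissatisfaction or any adverse event, the data collection will cease". The paragraph opens by addressing patient participants. The sentences after it deal with distress only. They let the patient end the session, finish it another day or withdraw consent, and they add referral when distress is moderate or severe. Ending a participant's involvement appears separately, for an event judged to be a serious adverse event.

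The exit interviews are described elsewhere. Aim 1 is to "Identify barriers and facilitators for the storytelling intervention from the perspectives of the key stakeholders". The Data Collection/Analysis section says that, two weeks after the story enters the health record, "both patient and nurse will be contacted for exit interviews to collect information about barriers and facilitators of the intervention". The Human Subjects section says that "the patient will answer exit interview questions to capture their experience of the storytelling intervention". The eligibility text in section IV.B gives the reason for enrolling a broad range of racial and ethnic groups, which includes "to collect acceptability data from a variety of groups". Sources of Materials gives the planned numbers: "24 for the patient exit interviews, 12 for the nurse exit interviews". The consent text mentions "the possibility of being selected to participate in the optional qualitative exit interviews", so 24 patient exit interviews is a ceiling.

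**The concern.** Dissatisfaction is listed as a trigger in its own right beside distress and adverse events, and the stop is worded as mandatory. The trigger covers any interview data, with no exception for the exit interview. A patient who says the story misrepresented them, or that no nurse read it, is voicing dissatisfaction and is also supplying what Aim 1 seeks.

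If the rule were applied in that way, the loss would be one-sided. Satisfied patients would finish their interviews, while critical patients would be stopped before the follow-up questions that explain what went wrong. The Expected Outcomes text relies on "Understanding of the patterns of barriers and facilitators of the storytelling experience from the perspectives of the key stakeholders" to shape the intervention, so thinner material from critical patients could leave its weaknesses less well understood.

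**Working it through.** No sample-size or error-rate formula applies. The check compares passages and makes one count.

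**Count.** From Sources of Materials: 24 storytelling + 24 patient exit + 12 nurse exit = 60 interviews, which matches the protocol's stated total. Exit interviews: 24 + 12 = 36. The paragraph concerns patients, so at most 24 of the 36 are exposed. The number affected lies between 0 and 24, and the protocol gives nothing to narrow it. These are counts of exposure and do not measure an effect.

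**What dissatisfaction refers to.** No passage defines it. The context points one way: the sentence sits under psychological risk, its neighbours in the list are distress and adverse events, and the paragraph closes by expecting such events to be rare. Negative comment on an intervention still being designed would not be expected to be rare in an interview held to elicit barriers. The term therefore fits an adverse reaction to participation much better than it fits criticism of the intervention. On that reading the number of exit interviews affected is 0.

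**What ceases.** The candidates are the session, the participant's involvement, or the whole study. Ending involvement is tied to a serious adverse event, which is a later and more severe step. Authority to suspend or close a study is placed with the cancer center's monitoring committee in the Data and Safety Monitoring Plan. The next sentence speaks of finishing the interview at a return visit. Read as a graded sequence, the first step is the current session.

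**Whether other text narrows the trigger.** Patient burden (section IV.E) and Protections Against Risk both deal with distress and do not mention dissatisfaction. They do not resolve the wording. They also do not repeat the mandatory stop, so the broad reading rests on one sentence. The Exit Interview Guide is an appendix that is not shown.

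**Consequence on the literal reading.** Aim 1 is analysed by open coding and thematic analysis, with no planned frequency or comparison, so there is no estimate to bias. Material recorded before a stop remains. The investigator keeps field notes on each contact, and the team discusses active cases monthly, so a stop would be seen. A patient can also name a barrier without being dissatisfied, and those barriers are untouched. What could be lost is detail from the patients who were stopped.

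**The case for a change.** The strongest case for a change is that compliance is judged against the text. The monthly audit checks the investigator's adherence to the protocol. An investigator who continues with a critical patient could be said to deviate, and one who stops loses Aim 1 detail. The sentence also mentions psychometric assessment, while the data-collection sections describe no such assessment of patients, which suggests wording carried over from another study. A clarifying sentence would cost little.

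Part of this stands: the term and the scope are undefined, and no other passage settles them. It does not carry the point further. The principal investigator alone collects the interviews, and the Data Collection/Analysis section makes barriers their purpose. No separate interviewer would apply the risk paragraph against that purpose. The auditors are mentors on the same team and know that purpose. The protocol also provides for adjustment after team review if a problem appears.

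A clarification that changed conduct would have to narrow a protective stop for seriously ill inpatients, in a protocol that names perceived coercion as a concern. Choosing that rule is not a matter for statistical review. If the sentence were ever applied to criticism of the intervention, the two sections would have to be reconciled by those responsible for participant protection.

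**Conclusion.** The wording is loose, but no change to the plan is called for. On the reading that the context supports, none of the planned patient exit interviews is affected. On the literal reading up to 24 of 36 exit interviews are exposed, the number cut short is unknown, and the cost is depth in a qualitative analysis. This is a gap that the investigator would fill sensibly in practice.

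The conclusion rests on two assumptions: that dissatisfaction here means an adverse reaction to taking part, and that the principal investigator conducts all the interviews, as the protocol states. The first is an inference from context. The conclusion would weaken if the Exit Interview Guide, which is not shown, instructed that interviews stop when a patient criticises the intervention.

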### **Adequacy of Protection Against Risks**

#### **a. Recruitment and Informed Consent**

The PI will be solely responsible for screening, consenting and collecting all the interviews. The participants will have the opportunity to decline at anytime throughout the study. The PI will recruit, through convenience sampling, minority patients with life limiting illness. Study participants will be recruited through University of Colorado Hospital. The PI will meet round at least weekly on identified units and as needed with nursing care team members nurses at the hospital and provide updates on recruitment needs till recruitment is complete.

At the hospital, nurses will identify potential participants based on diagnoses and ethnicity. If any patients are identified, a nurse will deliver a flyer regarding the study to potential patients to obtain verbal consent taking precautions to notify the potential participant that participation in the study is totally voluntary and will not affect care. Once verbal consent is obtained, nursing team members will notify the PI of potential patients via secure encrypted e-mail. The PI will then arrange a convenient time to meet with potential patients to review the study protocols and obtain informed consent. At these initial meetings of the participant, the PI will complete the official screening, describe the study, review the informed consent, and discuss risks/benefits with the participant. If at this initial meeting, participant volunteers and meets inclusion/exclusion criteria, the PI and participant will sign the informed consent. After the informed consent is signed.

Recruitment will include the use of flyers being given to the nursing team members and posted in the medical-surgical units. The PI will ensure continual availability of flyers for the key recruitment stakeholders. These flyers will include a brief description of the study, inclusion criteria, and multiple avenues for contacting the PI, such as by e-mail or or phone. The PI will also communicate weekly with the nursing care teams to identify any potential concerns with the recruitment procedures. The PI will be present at nurse staff meetings) to answer questions in person for the key stakeholders. In addition, this presence within the staff meetings will also act as a reminder to care team members about the study and updates on the recruitment needs for the

study. (See letters of support by [name] and [name], UC Health Research Administration).

The written consent forms will inform patients and nurses about their own participation in study activities, including randomization, participation in the intervention, and data collection and the risks and benefits of participation. The consent form for the patient participants will also include a section describing the possibility of being selected to participate in the optional qualitative exit interviews to be scheduled after the intervention. Patients and nurses will receive

